9.4.3 ANALYSIS OF THE SECONDARY ENDPOINT(S)

Fluoride and calcium concentrations in saliva (secondary endpoints) will be determined from the samples collected at baseline and 16 min, 30 min, 61 min, 90 and 121 min (± 5 min) after rinsing with the assigned mouth rinse(s). The concentration at each individual timepoint will be compared between the two intervention groups. Also, the area under the curve of fluoride and calcium concentration in saliva versus time will be calculated and compared between the two intervention groups.

Calcium concentration in dental biofilm (primary efficacy endpoint) will be determined from the samples collected at baseline and 15 min, 60 min and 120 min (± 5 min) after rinsing with the assigned mouth

rinse(s). The concentration at each individual timepoint will be compared between the two intervention groups. Also, the area under the curve of calcium concentration in dental biofilm versus time will be calculated and compared between the two intervention groups.

Each set of data will be checked for normality of errors. If the data is not normal, it will be log-transformed. An analysis of variance will be conducted, considering as factors the participant (experimental block) and the treatment. The use of the participant as a source of variation aims solely to reduce unknown variability in the error. An alpha level of 5% will be used to determine significant differences between the two groups.

In case data were log-transformed to fit the statistical analysis, their geometric means and confidence intervals (calculated from the log-transformed data) will be presented.

If data is missing from one of the intervention groups, the rest of the participant data (from the other intervention) will be excluded from the analysis.

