3 OBJECTIVES AND ENDPOINTS

OBJECTIVES	ENDPOINTS	JUSTIFICATION FOR ENDPOINTS
Primary		
Determine the benefit of using a calcium rinse, before a fluoride rinse, to enhance fluoride retention in dental biofilm of individuals with hyposalivation.	Fluoride concentration in dental biofilm (fluid and solid phase) up to 2 h after rinsing with fluoride.	Dental biofilm can take up fluoride and release it for prolonged periods of time, like the hours in between oral hygiene procedures.
Secondary		

OBJECTIVES	ENDPOINTS	JUSTIFICATION FOR ENDPOINTS

Determine the benefit of using a calcium rinse, before a fluoride rinse, to enhance fluoride retention in saliva of individuals with hyposalivation.
	
 1. Fluoride concentration in saliva up to 2 h after rinsing with fluoride. 2. Calcium concentration in dental biofilm (fluid and solid phase) up to 2 h after rinsing with fluoride. 3. Calcium concentration in saliva up to 2 h after rinsing with fluoride. 	
 1. Salivary fluoride can be considered as a surrogate measure of fluoride availability in the mouth, because from saliva fluoride from rinses gets to dental biofilm. 2. Since a calcium rinse will be used in one of the treatments in this study, determination of calcium concentration in dental biofilm will be made to identify potential sources of fluoride retention (e.g. fluoride bound to calcium ions, calcium fluoride precipitation). 3. Salivary calcium can be considered as a surrogate measure of calcium availability in the mouth; since a calcium rinse will be used in one of the study treatments, salivary calcium will be determined.
Tertiary/Exploratory		

Determine the role of hyposalivation on the retention of fluoride in the mouth after a fluoride rinse
	
 1. Correlation between salivary flow rate and fluoride concentration in dental biofilm up to 2 h after a rinse. 2. Correlation between salivary flow rate and fluoride concentration in saliva up to 2 h after a rinse. 	
The correlation between salivary flow rate and fluoride in dental biofilm and saliva will be investigated to estimate how the flow rate affect these variables.

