The participant will be asked to suck and swallow any excessive saliva in his/her mouth and a plastic spatula will be used to scrape the buccal surfaces (facing the cheek) of the teeth in that quadrant of the mouth, collecting any dental plaque accumulated there. This collection is expected to take about 1 min. The pooled plaque sample will be immediately immersed in mineral oil to avoid desiccation. The plaque samples will then be centrifuged to separate the fluid and solid phases. The fluid will be collected using a micropipette, under microscope. Both samples – the fluid and the solids – will be analyzed for calcium and fluoride concentration using a colorimetric method (Arsenazo III reagent) and an ion-selective electrode, respectively.

5. Collection of saliva samples: On the 2nd and 3rd visits, participants will have unstimulated saliva samples collected for the analysis of fluoride and calcium. The collections will start at the following timepoints:
 - At the beginning of the session, immediately after biofilm collection
 - 16 min \pm 5 min after rinsing with the intervention group, immediately after biofilm collection
 - 30 min \pm 5 min after rinsing with the intervention group
 - 61 min \pm 5 min after rinsing with the intervention group, immediately after biofilm collection
 - 90 min \pm 5 min after rinsing with the intervention group
 - 121 min \pm 5 min after rinsing with the intervention group, immediately after biofilm collection

For saliva collection, participants will drool any produced saliva into a funnel attached to a tube, for 5 min. The collected sample will be analyzed for fluoride and calcium concentration before and after being centrifuged. An ion-selective electrode and the Arsenazo III reagent will be used in the determination of fluoride and calcium concentrations, respectively.

6. Rinsing with the intervention groups: On the 2nd and 3rd visits, participants will rinse with the assigned mouth rinse (fluoride only or a calcium followed by a fluoride rinse) for 1 min each. The rinses will be performed with 15 mL of the assigned products, as a normal mouth rinse. All rinses will be expectorated. At the end of the 1-min rinsing with the fluoride rinse, a chronograph will be set up to determine the following collections, starting 15 min after the rinse and ending at least 2 h later.

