9 STATISTICAL CONSIDERATIONS

9.1 Statistical Hypotheses

- **Primary Efficacy Endpoint:**
- Fluoride concentration in dental biofilm
 - Null hypothesis: A fluoride rinse preceded by a calcium rinse is not superior than a fluoride-only rinse in enhancing fluoride concentration in dental biofilm (fluid and solid phases) up to 2 h after mouth rinsing.
 - Alternative hypothesis: A fluoride rinse preceded by a calcium rinse is superior than a fluoride-only rinse in enhancing fluoride concentration in dental biofilm (fluid and solid phases) up to 2 h after mouth rinsing.
- **Secondary Efficacy Endpoints:**
- Fluoride concentration in saliva
 - Null hypothesis: A fluoride rinse preceded by a calcium rinse is not superior than a fluoride-only rinse in enhancing fluoride concentrations in saliva up to 2 h after mouth rinsing.
 - Alternative hypothesis: A fluoride rinse preceded by a calcium rinse is superior than a fluoride-only rinse in enhancing fluoride concentrations in saliva (fluid and solid phases) up to 2 h after mouth rinsing.
- Calcium concentration in dental biofilm
 - Null hypothesis: A fluoride rinse preceded by a calcium rinse is not superior than a fluoride-only rinse in enhancing calcium concentration in dental biofilm (fluid and solid phases) up to 2 h after mouth rinsing.

- Alternative hypothesis: A fluoride rinse preceded by a calcium rinse is superior than a fluoride-only rinse in enhancing calcium concentration in dental biofilm (fluid and solid phases) up to 2 h after mouth rinsing.
- Calcium concentration in saliva
 - Null hypothesis: A fluoride rinse preceded by a calcium rinse is not superior than a fluoride-only rinse in enhancing calcium concentration in saliva up to 2 h after mouth rinsing.
 - Alternative hypothesis: A fluoride rinse preceded by a calcium rinse is superior than a fluoride-only rinse in enhancing calcium concentration in saliva up to 2 h after mouth rinsing.
- Tertiary/exploratory Endpoints:
- Correlation between salivary flow rate and fluoride concentration in dental biofilm
 - Null hypothesis: There is no correlation ($\beta = 0$) between salivary flow rate and fluoride concentration in dental biofilm after rinsing with a fluoride mouth rinse.
 - Alternative hypothesis: There is a correlation ($\beta \neq 0$) between salivary flow rate and fluoride concentration in dental biofilm after rinsing with a fluoride mouth rinse.
- Correlation between salivary flow rate and fluoride concentration in saliva

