9.4 STATISTICAL ANALYSES

9.4.1 GENERAL APPROACH

Descriptive statistics: Data of fluoride concentration in saliva and dental biofilm tend to have a not-normal distribution. If that is the case in this study, these data will be presented as the geometric mean

(of log transformed data) and confidence interval (calculated from log transformed data). Data of calcium, if fitting normal distribution, will be presented as means and standard deviations. If not fitting normal distribution, the same approach for fluoride will be used.

Inferential tests: The comparisons between groups will be made using analysis of variance, having the volunteers as statistical blocks (source of variation). This is only to reduce known variability from the error calculation. One-tailed tests will be used to test for superiority of one treatment versus the other. The p-value will be set at 5%.

Before the analysis of variance, the normality of errors will be tested. It is expected that fluoride data is not normally distributed, and therefore a log transformation of data will be performed (which usually is adequate to normalize the data). The same approach will be used for the calcium data.

Besides the groups comparisons, the salivary flow rate will be correlated with the fluoride concentration in dental biofilm and saliva, to help understand the effect of flow rate on fluoride salivary clearance. For that, a regression analysis will be used to correlate the data of salivary flow with fluoride concentration (area under the curve of fluoride concentration over time) in saliva and dental biofilm. A significance level of 5% will be used in this analysis.

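### Each secondary superiority hypothesis is tested at several timepoints and by AUC at 5%, and the plan does not say which result decides; salivary fluoride gets six post-rinse tests

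*Combined protocol and SAP*

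**What the plan says.** Section 9.1 lists three secondary efficacy endpoints: salivary fluoride, biofilm calcium and salivary calcium. Each has one null and one superiority alternative covering the two hours after rinsing. Section 3 attaches an objective to the salivary endpoint: "Determine the benefit of using a calcium rinse, before a fluoride rinse, to enhance fluoride retention in saliva of individuals with hyposalivation".

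Section 9.4.3 takes saliva samples "collected at baseline and 16 min, 30 min, 61 min, 90 and 121 min" and biofilm samples at baseline and three later times. It compares the groups at each timepoint and again by AUC: "Also, the area under the curve of fluoride and calcium concentration in saliva versus time will be calculated and compared between the two intervention groups". Biofilm calcium has its own AUC comparison. The threshold is "An alpha level of 5% will be used to determine significant differences between the two groups". Section 9.4.1 sets the direction, "One-tailed tests will be used to test for superiority of one treatment versus the other", and the general threshold, "The p-value will be set at 5" per cent.

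Three further passages bear on what is tested:

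- Section 8.1, item 5, on saliva: "The collected sample will be analyzed for fluoride and calcium concentration before and after being centrifuged". Section 9.4.3 does not say which of the two readings is analysed.
- The salivary fluoride alternative in 9.1 reads "A fluoride rinse preceded by a calcium rinse is superior than a fluoride-only rinse in enhancing fluoride concentrations in saliva (fluid and solid phases", but its null names no phases.
- Section 9.4.3 labels biofilm calcium a primary efficacy endpoint. The synopsis and sections 3, 4.1 and 9.1 make it secondary.

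I found no statement of a deciding test, a testing order or a multiplicity rule for these endpoints. The exploratory label is attached only to the flow-rate correlations.

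**The concern.** A hypothesis about salivary fluoride over two hours needs one pre-named result that settles it. Here six post-rinse results bear on the same hypothesis, each at the full 5%. If they disagree, for example if one timepoint is significant and the AUC is not, the plan gives no basis for saying whether superiority was shown. That choice would then be made after the data are seen.

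Salivary fluoride is where this matters. It carries its own benefit objective, and section 3 justifies it as a surrogate for fluoride availability in the mouth. The two calcium endpoints are less exposed to a false claim: one treatment supplies calcium directly, so a true null for calcium is hard to credit.

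**Working it through.** **Plan's own figure.** The plan gives 5% per comparison. It states no error rate for a set of comparisons, so there is no such figure to reproduce.

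**Count of post-rinse tests** (timepoints from 9.4.3, phases from 9.1):

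- Salivary fluoride: 5 timepoints + 1 AUC = 6
- Salivary calcium: 5 + 1 = 6
- Biofilm calcium: 3 + 1 = 4 as 9.4.3 is worded, or 4 × 2 = 8 with the fluid and solid phases of 9.1
- Total: 6 + 6 + 4 = 16, or 6 + 6 + 8 = 20

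If the primary label on biofilm calcium in 9.4.3 were taken literally, 6 + 6 = 12 secondary tests would remain.

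**Error rate for salivary fluoride.** With six independent tests the chance of at least one false positive would be 1 − 0.95^6 = 26.5%. That is too high, because the AUC is built from the same timepoints. By the trapezoidal rule the intervals between 16, 30, 61, 90 and 121 min are 14, 31, 29 and 31 min, so the AUC weights the five readings by 7, 22.5, 30, 30 and 15.5.

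I therefore simulated the five within-participant differences and formed the AUC from them:

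- With complete pairs, analysis of variance with participant and treatment as factors is equivalent to a paired t-test. I used one-tailed 5%.
- Completers: 15, the evaluable number in 9.2.
- No treatment effect, normal differences, and equal correlation between timepoints. The documents give no correlation, so a range is shown.
- 200,000 replicates per row.

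| Assumed correlation | Any of 5 timepoints | Any of 5 timepoints or AUC | AUC alone |
|---|---|---|---|
| 0 | 22.6% | 23.9% | 4.9% |
| 0.3 | 19.6% | 20.0% | 5.0% |
| 0.5 | 17.0% | 17.1% | 4.9% |
| 0.8 | 12.0% | 12.0% | 5.0% |
| 0.9 | 9.8% | 9.8% | 5.1% |

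With all 20 participants completing, the third column is 23.8%, 19.7%, 17.0%, 11.9% and 9.6%. Adding the segment from baseline to 16 min, with the baseline difference set to zero, does not change these figures materially.

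The excess comes almost entirely from the separate timepoint tests. The AUC alone keeps the stated 5%.

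**The case against.** The strongest reply is that the plan contains no rule by which any one significant timepoint rejects the hypothesis. That is correct. Section 9.4.3 lists comparisons and links none of them to the 9.1 null. A reader might infer that a single timepoint suffices, but the text does not say so. The fault is silence about which result decides, and the percentages above apply only if that silence is filled in the most permissive way. Likewise, the plan's 5% is a per-comparison level, so it does not break a promised familywise rate.

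A reader might also infer that the family holds at least 20 tests and quote a chance of about 64% (1 − 0.95^20) for it. The documents do not support this. Twenty is one reading among several, since 9.4.3 alone gives 16; the percentage assumes independent tests; and it needs every calcium null to be true after a calcium rinse. A count of 32, from doubling the 12 saliva tests, needs both saliva readings to be tested. Section 8.1 says only that both are measured.

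Finally, this is a single-site phase 1 study of 20 people. Section 3 separates three tiers of endpoint and gives the secondaries explanatory roles. On that view secondary results are supportive by convention, and formal gating behind the primary is not required. I accept that gating is a choice. But 9.1 writes superiority hypotheses for the secondaries and reserves the exploratory label for a lower tier, so their supportive standing has to be stated.

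**Conclusion.** The point holds as a gap in specification. Each secondary hypothesis has several tests at one-tailed 5% and no named deciding result. For salivary fluoride, if any one of the six were accepted as superiority, the false-positive chance would be about 17% at a correlation of 0.5, ranging from 24% at 0 to just under 10% at 0.9. It exceeds 5% throughout that range. These figures rest on the assumed correlation, normal differences and the any-of-six reading. Figures for the whole secondary family carry little weight and should not be quoted as the size of the problem.

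A reader might go further and say that the plan authorises a salivary claim after a failed primary. It sets no such condition either way. A stated supportive role for the secondaries is enough to settle that.

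**What to change.** In 9.4.3:

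1. Name the post-rinse AUC as the single deciding test for each secondary hypothesis, in one prespecified saliva preparation and, for biofilm calcium, one prespecified phase.
2. Report the individual timepoints and the other preparation or phase as supportive estimates with intervals and no superiority claim.
3. State that secondary results support the primary and are not adjusted across endpoints.
4. Correct the label that makes biofilm calcium a primary endpoint.

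In 9.1, remove the mention of fluid and solid phases from the salivary fluoride alternative so that it matches its null.

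A fixed sequence behind the primary is optional. It would first need one named primary test in 9.4.2, which at present compares three post-rinse timepoints and an AUC without choosing among them. The order of the secondaries would then be for the sponsor to justify.

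The change is to wording only and adds no samples, participants or assays. The cost is that a lone significant saliva timepoint could no longer be claimed as superiority, though it would still be reported as an estimate.

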10 SUPPORTING DOCUMENTATION AND OPERATIONAL CONSIDERATIONS

10.1 REGULATORY, ETHICAL, AND STUDY OVERSIGHT CONSIDERATIONS

10.1.1 INFORMED CONSENT PROCESS

An informed consent describing in detail the study intervention, study procedures, and risks are given to the participant and written documentation of informed consent is required prior to starting intervention/administering study intervention.

10.1.1.1 CONSENT PROCEDURES AND DOCUMENTATION

Informed consent is a process that is initiated prior to the individual's agreeing to participate in the study and continues throughout the individual's study participation. Consent forms will be Institutional Review Board (IRB)-approved and the participant will be asked to read and review the document. The investigator will explain the research study to the participant and answer any questions that may arise. A verbal explanation will be provided in terms suited to the participant's comprehension of the purposes, procedures, and potential risks of the study and of their rights as research participants. Participants will have the opportunity to carefully review the written consent form and ask questions prior to signing. The participants should have the opportunity to discuss the study with their family or surrogates or think about it prior to agreeing to participate. The participant will sign the informed consent document prior to any procedures being done specifically for the study. Participants must be informed that participation is voluntary and that they may withdraw from the study at any time, without prejudice. A copy of the informed consent document will be given to the participants for their records. The informed consent process will be conducted and the form signed, before the participant undergoes any study-specific procedures. The rights and welfare of the participants will be protected by emphasizing to them that the quality of their medical care will not be adversely affected if they decline to participate in this study.

10.1.2 STUDY DISCONTINUATION AND CLOSURE

This study may be temporarily suspended or prematurely terminated if there is sufficient reasonable cause. Written notification, documenting the reason for study suspension or termination, will be

provided by the suspending or terminating party to study participants. If the study is prematurely terminated or suspended, the Principal Investigator (PI) will promptly inform study participants, the Institutional Review Board (IRB), and sponsor and will provide the reason(s) for the termination or suspension. Study participants will be contacted, as applicable, and be informed of changes to study visit schedule.

Circumstances that may warrant termination or suspension include, but are not limited to:

- Determination of unexpected, significant, or unacceptable risk to participants
- Demonstration of efficacy that would warrant stopping
- Insufficient compliance to protocol requirements
- Data that are not sufficiently complete and/or evaluable
- Determination that the primary endpoint has been met
- Determination of futility

10.1.3 CONFIDENTIALITY AND PRIVACY

Participant confidentiality and privacy is strictly held in trust by the participating investigators, their staff, and the sponsor and their interventions. This confidentiality is extended to cover testing of biological samples in addition to the clinical information relating to participants. Therefore, the study protocol, documentation, data, and all other information generated will be held in strict confidence. No information concerning the study or the data will be released to any unauthorized third party without prior written approval of the sponsor.

All research activities will be conducted in as private a setting as possible.

The study participant's contact information will be securely stored at each clinical site for internal use during the study. At the end of the study, all records will continue to be kept in a secure location for as long a period as dictated by the reviewing IRB, Institutional policies, or sponsor requirements.

10.1.5 DATA HANDLING AND RECORD KEEPING

10.1.5.1 DATA COLLECTION AND MANAGEMENT RESPONSIBILITIES

Data collection is the responsibility of the clinical trial staff, under the supervision of the principal investigator. The investigator is responsible for ensuring the accuracy, completeness, legibility, and timeliness of the data reported.

All source documents should be completed in a neat, legible manner to ensure accurate interpretation of data.

Hardcopies of the study visit worksheets will be provided for use as source document worksheets for recording data for each participant enrolled in the study.

10.1.5.2 STUDY RECORDS RETENTION

10.1.6 PROTOCOL DEVIATIONS

A protocol deviation is any noncompliance with the clinical trial protocol. The noncompliance may be either on the part of the participant, the investigator, or the study site staff. As a result of deviations, corrective actions are to be developed by the site and implemented promptly.

It is the responsibility of the principal investigator to use continuous vigilance to identify protocol deviations. All deviations must be addressed in study source documents. Protocol deviations must be sent to the reviewing Institutional Review Board (IRB) per their policies. The principal investigator is responsible for knowing and adhering to the reviewing IRB requirements.

